This protocol describes a prospective, randomized, double-blind controlled trial comparing TSP alone to the combination of TSP with cathflo activase for achieving optimal results with pleurodesis for recurrent pleural effusion. Patients who sign informed consent will be randomly assigned to receive either TSP alone (talc, 5 gm in 50 ml NS) with placebo (50 ml NS) or TSP with cathflo activase (4 mg in 50 ml NS) through the chest pleural catheter. Follow-up lasts for three months. The primary outcome is achievement of a “Radiographically Satisfactory Pleurodesis” (RSP) by day three post-procedure, defined as chest tube drainage of less than 100 cc over 24 hours *and* a chest x-ray showing similar or less pleural space opacification than on the day TSP was performed (baseline, day 0). Secondary outcomes include the proportion of patients who achieve RSP, time needed to achieve RSP, duration of chest tube drainage, length of hospital stay after initiation of TSP, proportion of patients requiring repeat TSP, change in serum hemoglobin during therapy, objective assessments of pain and dyspnea, and potential complications. The incremental cost effectiveness of talc slurry pleurodesis with cathflo activase compared to without cathflo activase will be assessed using a static decision tree model, which will be constructed using the TreeAge Pro software. This study will recruit 136 patients, with an interim analysis for efficacy after 50 patients, and aims to help develop the future standard for management of patients requiring pleurodesis for their symptomatic pleural effusion.

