### **4.2. Secondary Objectives and Hypotheses**

Secondary hypotheses for this trial are that cathflo activase supplementation for TSP:

1. Is safe
2. Does not inhibit pleurodesis
3. Reduces the incidence of recurrence of pleural effusion
4. Reduces the incidence of incomplete pleurodesis (presence of loculated effusions)
5. Shortens the time to achieve pleurodesis.
6. Does not increase pain associated with TSP
7. Improves the patient's subjective assessment of dyspnea
8. Does not prolong chest tube drainage or length of hospitalization
9. Is as cost-effective as TSP alone

Secondary objectives for this trial are:

1. To determine if giving cathflo activase with TSP is associated with a higher incidence of complications compared to TSP with placebo.
2. To determine if giving cathflo activase with TSP improves pleural fluid drainage compared to TSP with placebo.
3. To determine if giving cathflo activase with TSP is associated with a greater decline in serum Hemoglobin and/or incidence of blood transfusion compared to TSP with placebo.
4. To determine if giving cathflo activase with TSP is associated with an increased incidence of repeat pleurodesis compared to TSP with placebo.
5. To determine if giving cathflo activase with TSP is associated with a lower incidence of recurrence of pleural effusion compared to TSP with placebo.
6. To determine if giving cathflo activase with TSP is associated with a lower incidence of pleural fluid loculations compared to TSP with placebo.
7. To determine if giving cathflo activase with TSP is associated with a shorter time to RSP in patients with MPE compared to TSP with placebo.
8. To determine if giving cathflo activase with TSP is associated with a shorter time to RSP in patients with benign pleural effusion compared to TSP with placebo.
9. To determine if giving cathflo activase with TSP is associated with any difference in pain as measured by a standard visual analog pain scale compared to TSP with placebo.
10. To determine if giving cathflo activase with TSP is associated with any difference in scoring on a visual analog scale for measurement of dyspnea compared to TSP with placebo.
11. To determine if giving cathflo activase with TSP is associated with shorter duration of chest tube drainage compared to TSP with placebo.
12. To determine if giving cathflo activase with TSP is associated with a short length of hospital stay after TSP compared to TSP with placebo.

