## 8. PROCEDURES

Figure 1 shows the proposed workflow through the trial. Following the informed consent, each participant is assigned a unique study number and baseline data will be collected before randomization. At this point the research nurse will briefly explain the procedure and familiarize the participant with the Visual Analogue Scale (VAS) system for dyspnea (Appendix I) and pain (Appendix II). Trial treatment will be delivered by means of either a pigtail chest tube (size 10-14 Fr) or PleurX® catheter at bedside after randomization. Outcome measures will be assessed daily until the chest tube is removed and at routine follow-up visits at approximately 14 days, 28 days and three months after the day of procedure as outpatients if the patient has been discharged. While the chest tube is in place, daily symptom assessment will be performed, and daily chest x-ray (PA and lateral when possible) and 24-hour drain output will be recorded (Appendix III) to determine if RSP has been achieved, or if further intervention is indicated.

RSP is defined as chest tube drainage less than 100 cc over the previous 24 hours and a chest x-ray showing similar or decreased pleural space opacification compared to the baseline chest x-ray done the day of pleurodesis (day 0).

Objective determination of the chest x-ray finding will be based on the formal Radiology report in the medical record. If necessary, the findings will be clarified by personal communication between study personnel and the Radiologist reading the film. The algorithm for chest tube and pleural space management after TSP is specified in Figure 2. If RSP is not achieved on day 3, then management will be determined using the algorithm based on the chest x-ray findings and pleural drainage, and may include continued observation, repeat cathflo activase, chest CT, insertion of additional pleural drainage tubes, and repeat TSP with or without cathflo activase. At all follow-up visits after the chest tube has been removed, assessment will include chest x-ray and completion of the VAS for pain and dyspnea.

[figure not shown]
Figure 1. Proposed Workflow of the Trial

Assessments/tasks at visits:

- ◆ VAS scores for pain and SOB
- ◆ Drained volumes in 24 hours if the chest tube is still in place
- ◆ Serum hemoglobin if the chest tube is place
- ◆ CxR (PA and lateral)
- ◆ CT scan, as justified by the PI

Figure 2: Chest Tube Management Algorithm

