## 8.2. Assessments/Tasks

Following consent, a baseline assessment will be undertaken pre-randomization by a member of the trial team and entered into the REDCap system hosted at Office of Human Research of MHS. The following data will be recorded prior to randomization:

1. Patient demographics and physical characteristics
2. Mode of presentation, current diagnosis, cause of effusions (if known).
3. Medical history and current medication.
4. Previous pleural interventions.
5. Symptoms, including pain and SOB according to a visual analog scale (VAS) (Appendix I, II).
6. Pleural fluid biochemical and cytological test results
7. Baseline hemoglobin (day of or day before TSP)
8. Baseline (day of or day before TSP) CxR and chest CT (if available) findings.

After randomization and TSP with or without cathflo activase, all patients will have daily follow-up until the chest tube is removed, and at 14 and 28 days, and three months after TSP. At all visits, the following data will be recorded:

1. VAS for chest pain and SOB will be documented (Appendix I, II).
2. CxR (PA and lateral preferred).
3. Drained pleural volumes in 24 hours (if the chest tube is still in place).
4. Serum hemoglobin (only for inpatient visits within three days of the pleurodesis procedure).
5. Repeat pleural interventions.
6. Chest CT scan, as justified by the principal investigator.

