## 8.3. Treatments/Interventions

The trial interventions are summarized in Figures 1 and 2 and described in detail below. The delivery of each of the treatment and its aftercare will be provided according to its usual practice protocols and are not specified in this trial. All patients will have a pigtail chest tube (size 10-14) inserted under image guidance, or PleurX® catheter placement. This is current practice for management of these patients. Prior to pleurodesis the chest tube will be managed to achieve the most complete fluid drainage possible as assessed by CxR and determined by the clinical team. In the case of uncertainty, chest CT will be used to confirm the drainage of fluid and adequate inflation of the lung.

For all subjects, talc slurry (sterile talc, 5 gm, mixed with lidocaine, 20 mg, diluted in sterile saline to a total volume of 100 mL and dispensed into two 60 mL luer lock syringes, prepared by MHS Pharmacy Department) will be instilled through the chest tube at bedside. This will be followed immediately by instillation of either placebo (arm 1: 50 mL normal saline) or study drug (arm 2: cathflo activase, 4 mg, suspended in 50 mL normal saline). This syringe will be prepared by the MHS Pharmacy Department based on the randomization results and coded so that neither the administering clinical team nor the patient will be able to discern to which arm the patient has been assigned. The chest tube will be clamped with orders written to unclamp in 12 hours and insure

the tube is connected to a pleural drainage system (e.g. Pleurevac®) set for standard suction of -20 cm H2O. Daily assessments will be performed until the chest tube is removed. These include drainage volume over 24 hours, CxR, and pain and dyspnea scores.

Drainage volume over the prior 24 hours will be recorded daily using the Bedside Pleural Drainage Record. If the volume is less than 100 cc/24 hours for day 3 (defined as the third 24-hour period following TSP) and the CxR on day 3 shows the pleural space is the same or better than baseline, then the chest tube will be removed. If the chest tube is not removed, management will be according to the algorithm in Figure 2, and may include: continued monitoring, chest CT to evaluate for residual loculated effusion, cathflo activase to evacuate undrained effusion, or repeat TSP with or without cathflo activase.

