## **9.0 STATISTICAL METHODS**

### **9.1. Primary and Secondary Outcome measures**

The primary outcome measure is the proportion of patients with successful pleurodesis at day 3 after administration of TSP. Successful pleurodesis is defined as “radiographically satisfactory pleurodesis” (RSP), as evidenced by 1) chest x-ray demonstrating similar or decreased amount of pleural fluid/opacification compared to day 0 (day pleurodesis is performed) and 2) drainage

of less than 100 ml of fluid over the preceding 24 hours. Chest x-ray results will be scored on a three-point scale (-1, 0, +1) based on comparison of pleural space opacification on the side of the TSP to baseline:

1. Worse (-1): Pleural space opacification is worse, suggesting residual undrained fluid or reaccumulation of loculated fluid.
2. Same (0): Pleural space opacification similar to baseline.
3. Better (+1): Pleural space opacification is better, suggesting less pleural fluid than at baseline.

The secondary outcome measures will include the following:

1. Proportion of patients with RSP at any time after TSP
2. Duration of chest tube drainage
3. Days to achieve RSP
4. Pain and dyspnea scores as assessed by a visual-analogue scale (on a scale from 0 to 100 mm, with a score of 0 indicating a complete absence of symptoms and a score of 100 maximum symptoms).
5. Proportion of patients requiring repeat pleurodesis
6. Proportion of patients requiring additional chest tube
7. Change in serum hemoglobin levels within three days of cathflo activase
8. Length of hospital stay (in days) after TSP.
9. All hospital costs associated with both treatment arms.

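### The hemoglobin outcome in Section 9.1 does not deliver its own objective: transfusion is not listed, values after a transfusion have no rule, and the time anchor is misworded

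*Combined protocol and SAP*

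**What the plan says.** Objective 3 in Section 4.2 has two parts, a "greater decline in serum Hemoglobin and/or incidence of blood transfusion", each compared with TSP plus placebo. Section 9.1, item 7, carries one of them: "Change in serum hemoglobin levels within three days of cathflo activase". Transfusion is not in the Section 9.1 list, nor among the data that Section 8.2 says are recorded at visits. Section 9.2 assigns a t-test to numerical variables and a chi-square or Fisher test to categorical ones, at one-sided 0.05. It has no rule for hemoglobin measured after a transfusion.

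The documents describe the hemoglobin window in four ways:

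- Abstract (2.0): "change in serum hemoglobin during therapy".
- Section 8, list under Figure 1: "Serum hemoglobin if the chest tube is place".
- Section 8.2, follow-up list: "Serum hemoglobin (only for inpatient visits within three days of the pleurodesis procedure").
- Section 9.1: three days counted from cathflo activase.

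The baseline is the same for everyone: "Baseline hemoglobin (day of or day before TSP"). So is the time of instillation. Section 8.3 says of the talc: "This will be followed immediately by instillation of either placebo (arm 1: 50 mL normal saline) or study drug".

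**The concern.** Section 11.1 names bleeding as one of only two risks that the combination adds to talc alone. Hemoglobin change is the only bleeding-related measure among the listed outcomes. Transfusion both marks a bleed and raises the hemoglobin that is used to measure it. Section 9.1 does not say whether the lowest, the last or the day-3 value counts, so an analyst could follow the plan and use a value that transfusion has partly restored. The patients who bled most would then be recorded with some of the smallest falls. A null hemoglobin result could be cited in support of the first secondary hypothesis, on safety, although treatment of the bleeding had blunted the measure.

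The anchor adds ambiguity. Placebo patients do not receive cathflo activase as randomized treatment. Read literally, their clock would start only with a later non-randomized dose, which Section 8.3 allows when the tube stays in: "cathflo activase to evacuate undrained effusion, or repeat TSP with or without cathflo activase".

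**Working it through.** **Is there a common time zero?** Yes. Baseline (8.2) is tied to TSP in all patients, collection (8.2) covers three days from pleurodesis in all patients, and placebo or study drug follows the talc at once (8.3). Replacing the drug name by TSP in Section 9.1 gives both arms one window. The list under Figure 1 differs from Section 8.2 mainly after day 3, when a tube may still be in place. Those later values play no part in a three-day outcome.

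**The plan's own figure.** The documents give no SD, event rate or power for hemoglobin or bleeding. The only figure to reproduce is the primary sample size (6.1: 60% v 80%, one-sided 5%, 80% power, 5% loss).

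- n per arm = [1.645·√(2·0.70·0.30) + 0.842·√(0.60·0.40 + 0.80·0.20)]² / 0.20² = (1.066 + 0.532)² / 0.04 = 63.9, so 64.
- 64 / 0.95 = 67.4, so 68 per arm and 136 in total, as stated.
- Evaluable per arm after 5% loss: 68·0.95 = 64.6, taken as 65.

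**Illustration of the transfusion effect (all hemoglobin inputs are assumptions).** Let e be the excess proportion who bleed on cathflo activase (none on placebo), L = 3 g/dL the loss, r the amount restored before the analyzed value, and s the SD of change in other patients. The test is one-sided toward a greater fall on cathflo activase.

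- Mean difference: d = e·(L − r).
- SE = √{[2s² + e(1 − e)(L − r)²] / 65}.
- Power = Φ(d/SE − 1.645).

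Worked case, e = 0.10 and s = 1.0:

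- r = 0: d = 0.30, SE = √[(2 + 0.81)/65] = 0.208, d/SE = 1.44, power 42%.
- r = 2: d = 0.10, SE = √[(2 + 0.09)/65] = 0.179, d/SE = 0.56, power 14%.
- r = 3: d = 0, power 5%, which equals alpha.

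Power with nothing restored / with 2 g/dL restored:

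| Excess bleeding | d (g/dL) | s = 0.8 | s = 1.0 | s = 1.5 |
|---|---|---|---|---|
| 1 point | 0.03 / 0.01 | 8% / 6% | 7% / 6% | 6% / 5% |
| 2 points | 0.06 / 0.02 | 11% / 7% | 9% / 6% | 8% / 6% |
| 5 points | 0.15 / 0.05 | 24% / 10% | 19% / 9% | 14% / 7% |
| 10 points | 0.30 / 0.10 | 51% / 17% | 42% / 14% | 28% / 10% |

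**Which rows are plausible?** Section 11.1 reports no bleeding of clinical significance in more than 300 doses. If doses are treated as independent, the one-sided 95% upper bound is 1 − 0.05^(1/300) = 1.0% per dose. That points to the top two rows, where a comparison of means has little power with or without restoration.

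**Would a test on the transfusion proportion do better at those rates?** Not as a test. With 65 per arm, 4 v 0 gives a one-sided Fisher p of (65·64·63·62)/(130·129·128·127) = 0.060. The next step, 5 v 0, gives 0.060·61/126 = 0.029. So at least five events against none are needed, while 2% of 65 is 1.3 patients. The proportion is useful because it counts events that a mean dilutes, and it can carry a confidence limit: 0 of 65 has a one-sided 95% upper bound of 1 − 0.05^(1/65) = 4.5%.

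**The case against.** The strongest reply is that this is an omission in one secondary outcome and not a biased analysis. Five points deserve an answer.

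- *Timing.* A reader might infer that the placebo arm has no defined window and that this conceals bleeding. Sections 8.2 and 8.3 do not support that. The anchor is a slip in wording and hides nothing by itself.
- *Post-transfusion values.* No section says they will be used. Hemoglobin is recorded at daily inpatient visits within the window, so pre-transfusion values will often exist. This stands: the bias is conditional on a choice that the plan leaves open.
- *Other routes.* A reader might infer that bleeding would go undetected. Adverse events and serious adverse events are collected (11.1), hemodynamics and hematocrit are monitored (11.2), and objective 1 compares complications. These routes can bring a bleed to light. However, no bleeding definition and no specific comparison between arms appears in Sections 9.1 or 9.2. Transfusion may be on the study datasheet (Appendix IV), which is not in the text available here.
- *Size.* A large loss of power needs bleeding rates well above the center's reported experience. This also stands, although that experience is informal and counts doses, not trial patients.
- *The remedy.* A lowest value tends to be lower when more samples are taken, and sampling is for inpatients only, so earlier discharge in one arm would give it a shallower minimum. Stopping at the first transfusion also drops later bleeding. Both points are fair, and the fix has to deal with them.

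**Conclusion.** The concern holds as a gap between objective and outcome. Objective 3 asks about hemoglobin decline and transfusion, and Section 9.1 lists only the first, with no rule for the values that transfusion alters. If post-transfusion values are used and there is a real excess of bleeding, the difference between arms shrinks in proportion to the amount restored, by two thirds when 2 of 3 g/dL return. That direction does not depend on the assumed rates, but the loss of power does: 42% to 14% at a 10-point excess (SD 1.0), and 7–9% to about 6% at 1 to 2 points.

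At rates near those in Section 11.1, the main limit is the low power of a mean-hemoglobin test, and transfusion adds little to it. This is a further reason to report the transfusion proportion, as a count with a confidence limit and without any expectation of a significant test. The documents do not support the stronger reading that the outcome as written conceals bleeding. They are silent on the value used, the time anchor is recoverable, and adverse event reporting remains. The correction is still worthwhile because it costs little and settles, before unblinding, a choice that could weaken a safety conclusion.

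**What to change.** Replace Section 9.1, item 7, with a definition that applies to both arms:

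1. Change from baseline hemoglobin (day of TSP or the day before) to the lowest value within three days of TSP, using only values taken before any transfusion.
2. In Section 9.2, compare arms by a linear model of that change with baseline hemoglobin as covariate, in place of the unadjusted t-test. The baseline is already collected.
3. List the proportion of patients transfused in the same three days as a paired secondary outcome, tested by the chi-square or Fisher test already in Section 9.2 and shown with a confidence interval. This pairing keeps in view patients whose bleeding continued after a first transfusion.
4. Report the number of hemoglobin samples per patient by arm, so that a difference in sampling or discharge can be seen when the lowest values are read.
5. Reconcile the hemoglobin windows in the Abstract, the list under Figure 1, Section 8.2 and Section 9.1.

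Cost: an amendment of wording, and transfusion dates taken from the medical record if the datasheet does not already hold them. No additional blood tests are needed. Two limits remain. The lowest value still depends on how often patients are sampled. A transfusion given for a reason other than bleeding will count in either arm, which adds noise but, under blinding, should not favor one arm.

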## 9.2. Statistical Analysis Plan

Statistical summaries and analyses of data will be performed at MHS. Descriptive analysis will be performed for all data including means and standard derivation or medians for continuous variables and proportions for categorical variables. Comparison of outcomes between the two arms will be performed using t-test for numerical variables and Pearson  $\chi^2$ -test or Fisher's exact for categorical variables, and a one-sided p-value of 0.05 will be considered to be statistically significant.

The main analysis for primary outcome will be performed as per the intention-to-treat principle, and will include all the randomized participants with an observed outcome.(26) The primary outcome of the success rate of pleurodesis at day 3 will be analyzed using  $\chi^2$ -test. Time to symptomatic fluid recurrence following initial successful pleurodesis within 3 months follow-up period will be analyzed using a log-rank test. An interim analysis will be performed by the Memorial Healthcare System Quality and Safety Steering committee under [name] (currently officially the DSMB for MHS) after 50 patients are randomized in order to test for efficacy. The O'Brien-Fleming stopping rule will be used, which requires a P value of < 0.0088 (1-sided) for the primary outcome in order to stop at the interim analysis. The O'Brien-Fleming rule requires a P value of < 0.05 (1-sided) at the final analysis in order to declare a statistically significant difference in the primary outcome.(27) Analyses will be performed with the use of Prism 7.0 or SPSS 26 software.

Costs will be those related to study medications, initial hospital stay, and subsequent hospitalizations. All costs will be reported in US dollars and in 2020 prices. Cost data for both

arms will be obtained from MHS Strategic Financial Support Services. Outcomes will be measured in terms of probability of treatment success and/or complication, and utility of health states, which will be transformed to quality-adjusted life years (QALYs), calculated as the success rate of pleurodesis from each patient at day 3 after administration of TSP combined with pain and dyspnea scores.

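### One-sided 0.05 testing does not fit the non-directional pain and dyspnea objectives, and a non-significant test of difference cannot support the safety and no-harm hypotheses

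*Combined protocol and SAP*

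**What the plan says.** Section 9.2 names the t-test, Pearson chi-square and Fisher's exact test for comparing the arms and adds that "a one-sided p-value of 0.05 will be considered to be statistically significant". It names no tail for any secondary outcome. The planned summaries are means, standard deviations, medians and proportions. No between-arm confidence interval and no non-inferiority or equivalence margin appears.

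Section 4.2 holds two lists that do not always ask the same question.

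- **Pain.** Objective 9 looks for "any difference in pain as measured by a standard visual analog pain scale"; hypothesis 6 is "Does not increase pain associated with TSP".
- **Dyspnea.** Objective 10 looks for "any difference in scoring on a visual analog scale for measurement of dyspnea"; hypothesis 7 is "Improves the patient's subjective assessment of dyspnea".
- **Drainage time and hospital stay.** Hypothesis 8 is "Does not prolong chest tube drainage or length of hospitalization"; objective 11 asks whether the drug "is associated with shorter duration of chest tube drainage compared to TSP with placebo", and objective 12 whether it "is associated with a short length of hospital stay after TSP".
- **Other no-harm or equivalence hypotheses.** Hypothesis 1 asserts safety, hypothesis 2 that pleurodesis is not inhibited, and hypothesis 9 that the combination is as cost-effective as talc alone.

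Most other objectives carry a direction. Objective 13 (cost) has none. The additional chest tube outcome in Section 9.1 has none there either, although Section 11.3 expects fewer additional pleural interventions.

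**The concern.** There are two separate problems.

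The first is sidedness. A one-sided test answers a question about one direction only, and objectives 9 and 10 ask about both. An analyst would have to take the tail from the hypotheses, which leaves the other direction untested, or from the data, which doubles the error rate.

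The second is what a null result may be taken to mean. Five hypotheses assert no harm or equivalence, but the plan provides only tests of difference and does not say what result would support those hypotheses. The obvious reading is that p > 0.05 shows no harm, and it does not. The protocol itself names the harms at issue: Section 3.1 says that fibrinolysis could make pleurodesis fail, and Section 11.1 names an increased risk of bleeding.

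**Working it through.** **Sample size (Section 6.1).** Inputs: 60% versus 80%, one-sided 0.05, 80% power, 5% loss. With pooled variance and no continuity correction:

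n = [1.645·√(2·0.7·0.3) + 0.842·√(0.6·0.4 + 0.8·0.2)]² / 0.20² = 63.9, so 64 per arm.

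64/0.95 = 67.4, so 68 per arm and 136 in total. The plan's figure is reproduced. The rest uses 64 evaluable per arm.

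**Sidedness for pain and dyspnea.** Section 9.1 gives a 0 to 100 mm scale but no SD. I assume SD 20, 25 and 30 mm and a true difference d = 10 mm. SE = SD·√(2/64).

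| Assumed SD (mm) | SE (mm) | One-sided, effect in tested direction: Φ(d/SE − 1.645) | One-sided, effect in other direction: Φ(−d/SE − 1.645) | Two-sided: Φ(d/SE − 1.96) |
|---|---|---|---|---|
| 20 | 3.54 | 0.88 | 0.000004 | 0.81 |
| 25 | 4.42 | 0.73 | 0.00005 | 0.62 |
| 30 | 5.30 | 0.60 | 0.0002 | 0.47 |

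If pain is tested toward harm (hypothesis 6), a 10 mm fall is flagged at most 0.02% of the time. The same holds for a 10 mm worsening of dyspnea tested toward benefit (hypothesis 7). If the tail is chosen after seeing which arm is higher, the two-sided error is 2 × 0.05 = 0.10.

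**What a non-significant result leaves open.**

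- *Hypothesis 6.* If pain truly rises by 10 mm, a one-sided test for harm is non-significant with probability 1 − 0.88, 1 − 0.73 or 1 − 0.60, that is 12%, 27% or 40%. With equal observed means, the 95% interval half-width 1.96·SE is 6.9, 8.7 or 10.4 mm.
- *Hypothesis 2, if the primary test does not succeed.* With both arms observed at the protocol's 60%, the half-width is 1.96·√(2·0.6·0.4/64) = 0.170. The interval runs from −17 to +17 points, so it does not exclude a true success rate on the combination about 17 points below control (about 43% against 60%).
- *Hypothesis 1.* Even with no event of a given kind among 64 treated patients, the one-sided 95% upper limit on its rate is 1 − 0.05^(1/64) = 4.6%.

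Hypotheses 8 and 9 have the same logical gap. The documents give no variance for drainage time, stay or cost, so I put no figure on them.

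**The case against.** **One-sided testing is legitimate, and most objectives are directional.** This stands. Complications, hemoglobin decline, repeat pleurodesis, recurrence, loculations, time to success, drainage time and stay all have a stated direction. A reader might infer that the primary test or N = 136 is unsound. The documents do not support that: the primary question is directional, and its sample size reproduces at one-sided 0.05.

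**Hypotheses 6 and 7 already supply a tail.** They do, and declaring those tails would remove the 10% error. It would still leave objectives 9 and 10 unanswered in one direction.

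**A superiority test can support a no-harm hypothesis.** Also true. A significant gain in success rate would support hypothesis 2, and significantly shorter drainage or stay would support the matching part of hypothesis 8. The problem is therefore limited to non-significant results. A reader might also see hypothesis 8 as contradicting objectives 11 and 12. It does not: shorter implies not prolonged, so the statements are nested.

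**The information is recoverable.** Largely so. With arm sizes, readers could rebuild intervals for proportions, and for means where SDs are reported, and an effect in the untested direction would show in the arm summaries. Adverse events are recorded and reported to the IRB. It would go too far to say that harm would be hidden; what is missing is a prespecified inference.

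**There is no sign of a bleeding problem.** Section 11.1 reports no clinically significant bleeding in more than 300 doses. That experience is uncontrolled, but nothing in the documents suggests an excess, and this point does not depend on one.

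**Cost-effectiveness is left to a model.** The Abstract assigns it to a decision tree. That yields an estimate, but no stated criterion for calling the arms equally cost-effective.

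**Conclusion.** The point holds for secondary and safety inference only. The one-sided rule cannot answer objectives 9 and 10: either one direction goes essentially untested (below 0.1% for a 10 mm effect) or the two-sided error is 10%. A non-significant result cannot support hypotheses 1, 6, 8 or 9, nor hypothesis 2 if the primary test does not succeed.

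The ±17 points rests on the protocol's own 60% and on 64 evaluable per arm. The visual analog scale figures rest on assumed SDs of 20 to 30 mm and an assumed 10 mm difference. They are indicative only, because scores are collected daily and at three later visits (Section 8.2) and no analysis time point is stated. The logical mismatch does not depend on these assumptions. This should be changed before unblinding, since either choice of tail, or of how to read a null result, could later be questioned as data-driven.

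**What to change.** Keep the one-sided primary test and N = 136. In Section 9.2:

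1. Test pain and dyspnea (objectives 9 and 10) two-sided at 0.05.
2. Report secondary and safety differences with two-sided 95% confidence intervals.
3. State that hypotheses 1, 2, 6, 8 and 9 are estimation aims described by those intervals, and that p > 0.05 will not be reported as showing safety or absence of harm. If the sponsor wants a formal claim, prespecify a margin instead.
4. State the tested direction for additional chest tube (Section 11.3 suggests fewer) and compare cost two-sided.
5. State that where a one-sided test is kept, the test decides significance and the 95% interval describes precision.

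Item 5 is needed because the two can disagree. For example, 47/64 versus 38/64 gives one-sided chi-square p = 0.046, but a Newcombe 95% interval of −2.3 to +29.4 points.

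The cost is SAP wording and some power. For a 10 mm difference, power for pain and dyspnea falls from 88%–60% to 81%–47% across the assumed SDs. Some no-harm hypotheses will be reported as inconclusive. A margin could also strain the sample size: purely as an illustration, a 10 mm margin at one-sided 0.05 and 80% power needs 2·SD²·(1.645 + 0.842)²/10² = 50, 78 or 112 per arm for SD 20, 25 or 30 mm, against 64 available.
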